9.3 Primary Efficacy Analysis

All efficacy analysis details in this section are provided for cohorts 1-3 analysis.

For cohort 4 analysis the same approach will be used. Any differences and additional analyses will be described in the SAP Addendum.

9.3.1 Primary Efficacy Estimand

The primary efficacy estimand will be the effect of each individual EDP1815 cohort compared to the pooled placebo group on the percentage of participants achieving EASI-50 at Week 16. The population summary measure of interest will be the odds ratio between each active EDP1815 treatment group and pooled placebo.

Intercurrent events will be accounted for in the following manner:

Table 1 Intercurrent Event Strategies for the Primary Estimand (EDPS1)

Intercurrent event		
Use* of Permitted TCS/TCI Therapy or Type 1 Prohibited Medications ¹	Study Discontinuation Before Week 16 Visit or Type 2 Prohibited Medications ² Use	Noncompliance or Unblinding or Other Protocol Deviations Affecting Efficacy Before Week 16

If <28 days before Week 16 visit: Composite strategy Participant will be considered a non-responder
 
If ≥28 days before Week 16 visit: Treatment policy strategy Data will be used as collected
	
If type 2 prohibited medication² used: Composite strategy Participant will be considered a non-responder from the date of medication start
 
If due to related** reason: Composite strategy Participant will be considered a non-responder from the time of treatment discontinuation in case of missing data
 
If due to non-related** reason: While-on-treatment strategy No replacement of missing data (data after treatment discontinuation will be used as collected)
	
Treatment policy strategy: Data will be used as collected

* Consider the last day with therapy for participant before Week 16.

** Treatment discontinuation reasons will be checked. Reasons related to study medication are lack of efficacy, treatment failure, adverse event (if related). Also, withdrawal of consent may be considered related to study medication based on the clarification text provided, that will be assessed by the Evelo team and provided in a separate spreadsheet. Non-related reasons are all other reasons.

¹Prohibited concomitant medications which may affect efficacy requiring the concomitant medication to be immediately discontinued where possible once the use is discovered. Such medications use will be recorded as protocol deviation. Classification will be provided by the sponsor in a separate spreadsheet.

²Prohibited concomitant medications which may affect efficacy requiring IMP discontinuation. Such medications use will be recorded as protocol deviation. Classification will be provided by the sponsor in a separate spreadsheet.

If multiple events occurred, composite and while-on-treatment strategies are prioritized over treatment policy strategy. If multiple events requiring composite and while-on-treatment strategies occurred, study discontinuation due to treatment related reason and type 2 prohibited medication

strategy will be prioritized. If data does not change after applying composite strategy (for example, there is a treatment discontinuation due to related reason event and scheduled visit after treatment discontinuation was performed and so data from this visit will not be replaced), other events strategies still may be applied.

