2. STUDY OBJECTIVE(S)

2.1. Primary Objectives

The study will compare four treatment regimens of EDP1815 with placebo in participants with atopic dermatitis who are using twice daily topical emollients.

The primary comparison of interest is the odds ratio for achievement of an EASI-50 response at Week 16. The primary trial objective is to show superiority of EDP1815 over placebo.

The primary comparison will be made using a treatment policy strategy with respect to study medication but without regard to treatment compliance or any changes in background therapy. A composite strategy will be used with respect to use of topical corticosteroid rescue therapy with any participants who use these less than 28 days prior to the Week 16 assessment being considered as non-responders. A composite strategy will also be used for participants who withdraw from the study prior to the Week 16 visit for reasons relating to study medication (e.g., related adverse event, lack of efficacy, requirement of for alternative therapy) also being considered as non-responders. A ‘while on treatment’ strategy will be used for participants who withdraw from the study prior to Week 16 for reasons considered unrelated to study medication, with the achievement of response at Week 16 being considered missing.

A number of supportive analyses to check the robustness of the primary estimand approach will be performed. These will consider

- Topical corticosteroid rescue therapy in the window of 2-4 weeks prior to study medication as having no effect and using the composite strategy only for use less than 14 days prior to the Week 16 visit
- Using a ‘while on treatment’ strategy for rescue medications with any Week 16 data collected less than 28 days after rescue medication use being considered missing.
- Using a ‘while on treatment’ strategy for discontinuation of the study for any reason before Week 16.
- Using a principal stratum strategy excluding participants who are non-compliant with respect to study medication or emollient use (<75% compliance), use a prohibited background therapy, take at least one dose of the incorrect study medication or who are unblinded prior to the end of the study.
- Using an alternative composite strategy for topical corticosteroid rescue therapy, with all participants who use any topical corticosteroid therapy at any time between Day 1 and Week 16 considered as non-responders at the Week 16 visit.

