11.6. Handling of Dropouts or Missing Data

Unless otherwise specified, missing data will be considered as missing at random and will be accounted for using mixed models for repeated measures, with all time points collected for the relevant endpoint included in the model.

Otherwise, missing data will not be imputed.

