5.3.4.2 Treatment-Emergent Adverse Events

An adverse event (AE) will be classified as ‘treatment-emergent’ if the onset date/time was on or after the start date/time of study treatment. Where dates or times are missing or partially missing, AEs will be assumed to be treatment-emergent, unless there is clear evidence (through comparison of partial dates/times, see [Section 7.3.1](#)) to suggest that the AE started prior to dosing.

AEs will be classified into the following study phases based on the onset date/time of the AE after any imputations:

- Pre-Treatment Phase: All AEs with onset date/time prior to the first dose of randomised study treatment
- Treatment Phase: All AEs with onset date/time at the time of or after the first dose of randomised study treatment (Day 1) up to and including the date of the last dose of treatment received.
- Follow-up Phase: All AEs with onset date after the date of the last dose of treatment received.

For participants who complete 16 weeks of dosing per protocol, the Treatment Phase will be from Day 1 to the Week 16 visit, and the Follow-up Phase will start after the Treatment Phase and last until their last day in the study. In all cases the day will be assumed to start at 00:00 hours and end at 23:59 hours. Adverse events occurring in both the Treatment Phase and Follow-up Phase are classified as treatment emergent.

The onset phase of all AEs will be included in the relevant data listings.

6 Sample Size

Cohorts 1-3

The sample size was calculated using the assumption that data from the placebo participants in the three cohorts can be pooled prior to comparison with the EDP1815 treatment groups. No adjustments for multiple testing have been made.

The primary efficacy endpoint is the achievement of EASI-50 at Week 16. The pooled placebo response rate is estimated to be approximately 25% and a doubling of this to 50% for EDP1815 would be considered as clinically meaningful.

Using a two-sided test at the 5% level of significance, 58 participants in each treatment group would give 80% power to detect a difference in one of the EDP1815 cohorts compared to the pooled placebo group. There would also be more than 90% power to compare the pooled EDP1815 group to the pooled placebo group.

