Under the assumption of a 20% drop-out of participants prior to Week 16 this will require a total of at least 73 participants to be enrolled in each treatment group. In order to allow for the 3:1 randomisation in each cohort this has been adjusted to 75 participants per treatment group to give a total of 300 participants recruited. With 75 EDP1815 participants and 25 placebo participants in each of the three cohorts.

Cohort 4

Using the same assumptions relating to the placebo rate, clinically meaningful difference, significance level, and drop-out rate as above for Cohorts 1-3, approximately 70 participants are required in each of the EDP1815 8.0×10^{10} and Cohort 4 Matched Placebo groups to provide approximately 80% power in detecting a difference between EDP1815 and placebo in Cohort 4.

In order to allow 50% of the placebo control group to be concurrent controls and 50% to be historic matched controls from Cohorts 1-3, a 2:1 randomization will be used to enroll 70 EDP1815 8.0×10^{10} subjects and 35 placebo participants to Cohort 4.

If sensitivity analyses indicate that pooling of the Cohort 4 placebo group with the Cohort 1-3 matched placebo data is inappropriate, then the power of the comparison between the Cohort 4 EDP1815 and placebo groups is approximately 65% if only Cohort 4 placebo participants could be used in the treatment comparisons.

7 General Considerations

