7.7 Visit Windows

All data will be reported according to nominal visits. For example, if a Week 2 visit occurred on Day 16 instead of the nominally expected Day 14 it will be reported and included in the summary statistics/statistical analyses for Week 2.

Scheduled visits which occur outside the protocol-specified visit window (e.g., if the Week 2 visit occurred on Day 19 outside of the Day 12-18 window), this will be noted as a protocol deviation but data collected will still be included in all summary and analysis tables.

Unscheduled visits and Early Termination visit will not be included in summary or analysis tables, unless they are baseline measurements, provide data towards a safety endpoint which looks at worst-case post-baseline, or if a visit is a rescue therapy unscheduled visit.

Week 20 visit will be included in the summaries, but no analysis will be done at this visit.

For the rescue therapy, subjects who started rescue therapy outside of a scheduled visit should complete assessments required for the rescue therapy unscheduled visit. This data will only be included in tables and figures in cases where the last off-rescue observation carried forward imputation method is used to account for the intercurrent event of rescue therapy.

All listings will include all collected data even if they are from an unscheduled visit.

8 Summary of Study Data

All continuous variables will be summarized using the following descriptive statistics: n (non-missing sample size), mean, SD, median, maximum and minimum. The frequency and percentages (based on the non-missing sample size) of observed levels will be reported for all categorical measures.

In general, all data will be listed, sorted by cohort (1, 2, and 3 for the cohorts 1-3 analysis and 1-4 for the final analysis), randomised treatment (Placebo, EDP1815), site number and participant number. Relevant listings will include whether the assessment was performed and the date, study day/visit and time of the assessment as applicable.

Unless otherwise specified below, all summary tables will be structured with a column for each treatment. Where appropriate, columns combining all placebo participants, all EDP1815 participants and an overall total column may also be presented.

For summaries of study disposition, demographic and baseline data and study treatment compliance, columns will be ordered and labelled as follows:

- Cohort 1 Placebo
- Cohort 1 EDP1815
- Cohort 2 Placebo
- Cohort 2 EDP1815

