9.3.3 Main Analytical Approach

The primary analysis will be performed using a logistic regression model. The model will include parameters for treatment group, baseline vIGA score and baseline EASI score. As described in [Section 9.2](#) additional covariates for baseline factors will be assessed using this model for inclusion in all efficacy models. Only Week 16 data will be included in the model.

Treatment will consist of 4 levels (all placebo, cohort 1 EDP1815, cohort 2 EDP1815, cohort 3 EDP1815). Baseline vIGA will consist of 3 levels (2, 3 and 4).

The following treatment differences will be estimated:

- Cohort 1 EDP1815 vs Pooled placebo
- Cohort 2 EDP1815 vs Pooled placebo
- Cohort 3 EDP1815 vs Pooled placebo
- Cohorts 2+3 EDP1815 vs Pooled placebo*
- All EDP1815 vs Pooled placebo*
- Cohort 2 EDP1815 vs Cohort 3 EDP1815**
- Cohort 1 EDP1815 vs Cohort 2 EDP1815**

* Comparisons between pooled EDP1815 groups and pooled placebo will be considered as secondary analysis.

** Comparisons between EDP1815 treatment groups will be considered as exploratory analysis.

The comparisons between pooled EDP1815 groups* and comparisons between EDP1815 treatment groups** will be done using contrasts (LSMESTIMATE statement) within the relevant SAS procedures.

The actual and predicted probability of EASI-50 response at Week 16 in each treatment group together with the estimated odds ratios and associated confidence intervals for each treatment difference will be displayed. P-values will be displayed for the comparisons of active treatment (individual and pooled) vs pooled placebo.

Vertical bar plots for the actual and predicted probabilities of EASI-50 at Week 16 for each treatment group will be plotted.

The primary analysis approach will be repeated using the 4 supplementary estimands described in [Section 9.3.2](#).

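### Non-related withdrawals are labelled while-on-treatment but left missing, so the primary odds ratio is a Week 16 complete-case estimate that ignores EASI already collected

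*SAP*

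**What the plan says.** SAP Table 1 (section 9.3.1) splits study discontinuation before Week 16 by reason. Related reasons (lack of efficacy, treatment failure, related adverse events, and consent withdrawals that the sponsor reclassifies) count as non-response. Every other reason is non-related. That class is given a while-on-treatment strategy with the rule "No replacement of missing data (data after treatment discontinuation will be used as collected". Protocol 2.1 uses the same label, "with the achievement of response at Week 16 being considered missing". The EDPS1 definition (SAP 7.1.2.1) likewise leaves these values missing.

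On the primary logistic regression, SAP 9.3.3 states: "Only Week 16 data will be included in the model". SAP 7.7 states: "Unscheduled visits and Early Termination visit will not be included in summary or analysis tables". None of its listed exceptions covers the post-baseline EASI of a non-related withdrawal. EDPS1 uses Early Termination values only in the last-off-rescue imputation of continuous endpoints, not for EASI-50 response.

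SAP 9.3.4 names the generalised linear mixed model (GLMM) of EASI-50 as a sensitivity analysis for the primary endpoint. SAP 9.4.2.2 fits it to all visits except Week 20, but allows earlier visits to be dropped, or the model to be replaced by a Week 16 logistic regression if that seems more suitable for the data.

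**The concern.** A while-on-treatment strategy takes the outcome observed up to the intercurrent event. Here nothing observed before withdrawal stands in for the response. The endpoint remains EASI-50 at Week 16, and the participant is absent from the model. The name therefore promises a quantity that the analysis does not estimate.

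The unused data exist. The schedule of assessments (Protocol Table 4-1) collects EASI at Weeks 2, 4, 8 and 12 and at the Early Termination visit. The clause about using data after treatment discontinuation has little to act on, because Protocol 5.4 ties stopping study drug to withdrawal from the study.

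At stake is the primary odds ratio. The non-related class is a residual one. It includes loss to follow-up, non-compliance and unreclassified consent withdrawals, some of which could track poor response. If they do so differently by arm, the complete-case odds ratio moves.

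**Working it through.** **Inputs.** From SAP section 6: "The pooled placebo response rate is estimated to be approximately 25% and a doubling of this to 50% for EDP1815"; "Using a two-sided test at the 5% level of significance, 58 participants in each treatment group would give 80% power"; "Under the assumption of a 20% drop-out of participants prior to Week 16 this will require a total of at least 73 participants". The planned size is 75 per EDP1815 cohort against 75 pooled placebo. The documents do not give the non-related withdrawal rate by arm or its link to response, so these are assumed below.

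**The plan's own figure.** With a mean rate of 0.375, n = [1.96·√(2·0.375·0.625) + 0.842·√(0.25·0.75 + 0.5·0.5)]² / 0.25² = 57.7, so 58 per arm (power 80.2%). Then 58/0.8 = 72.5, so 73. Both figures reproduce. The inflation itself treats drop-outs as removed from the analysis.

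**Illustration.** Assume true response rates p of 25% and 50% (OR 3.00) at both Week 12 and Week 16, a latent bivariate normal correlation of 0.7 or 0.8, and withdrawal between the two visits with probability dR for Week 12 responders and dN for non-responders. Let a and b be the Week 16 response probabilities given Week 12 response and non-response. Then

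complete-case rate = [p·a·(1−dR) + (1−p)·b·(1−dN)] / [p·(1−dR) + (1−p)·(1−dN)].

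At correlation 0.7, a = 0.602 and b = 0.133 on placebo, and 0.747 and 0.253 on active. At 0.8 they are 0.676 and 0.108, and 0.795 and 0.205.

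Worked case, correlation 0.7, placebo dN = 20% and dR = 5%: (0.25·0.602·0.95 + 0.75·0.133·0.80) / (0.25·0.95 + 0.75·0.80) = 0.2226/0.8375 = 0.266. If active drop-out is unrelated to response, its rate stays at 0.50 and OR = 1/(0.266/0.734) = 2.76.

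| Withdrawal pattern | Complete-case OR |
|---|---|
| Placebo loses non-responders (18-20% vs 4-5% of responders), active 8-10% at random | 2.70-2.80 |
| Active loses non-responders (20% vs 5%), placebo 10% at random | 3.27-3.32 |
| 20% vs 5% in both arms | 3.01 |
| No true effect (25% in both arms), active loses non-responders as in row 2 | 1.09-1.10 |

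With about 60 evaluable per arm, SE(log OR) = √(1/30 + 1/30 + 1/15 + 1/45) = 0.39. The shifts in the first two rows are ln(3/2.70) = 0.105 down to ln(3/2.80) = 0.069, and ln(3.27/3) = 0.086 up to ln(3.32/3) = 0.101. That is about 0.2-0.3 standard errors.

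**Effect on false positives.** Take no true effect (25% in both arms) and 75 randomised per arm. If d is the arm's drop-out and q the response probability of those who leave, the completer rate is (0.25 − d·q)/(1 − d). With q = 0 and 25% vs 15% drop-out (active vs placebo), the rates are 0.333 and 0.294, the OR is 1.20, and rejection is 7.5% instead of 5%. With q = 10% the same imbalance gives OR 1.12 and 6.0%. With q = 25%, so that leavers resemble completers, the OR is 1.00 whatever the imbalance.

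**Extreme bounds.** With completers at 50% and 25%, setting all missing values against or in favour of EDP1815 gives an OR of 2.24-3.55 at 5% missing, 1.70-4.21 at 10% and 1.00-6.00 at 20%. The last would require every drop-out to be non-related.

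**Planned safeguards (SAP 9.3.2, Table 2).** Supplementary estimands 1, 2 and 5 keep the same rule for non-related withdrawal. Estimand 4 does too, apart from its own exclusions. Estimand 3 sets all discontinuations to missing. None counts every withdrawal as non-response, and no multiple imputation or tipping-point analysis is listed.

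**Visit windows.** The ±3-day windows around Days 15, 29, 57 and 85 cover 4 × 7 = 28 of the 108 days from Day 2 to Day 109. An Early Termination visit on about three-quarters of those days would fall in no window.

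**The case against.** The best defence is that the operational rule is unambiguous and protocol and SAP agree on it, so only the label is loose. The plan already removes much response-driven withdrawal from the missing class: lack of efficacy, treatment failure, related adverse events and type 2 prohibited medication all count as non-response. The GLMM uses earlier scheduled responses, is valid under missing at random, and is listed for the top-level results. The shifts above are small against the standard error, and the first is towards the null. The illustration also favours imputation: withdrawal depends only on Week 12 status, and every leaver has a Week 12 value. Much of this stands, and it limits the size of the point. It does not remove it. The GLMM may be replaced by the same Week 16-only model on a judgement about the data, the direction of bias can equally favour the drug, and the Early Termination EASI remains unused.

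A reader might also infer a conflict with Protocol 11.6, which says that "missing data will be considered as missing at random and will be accounted for using mixed models for repeated measures". The documents do not support this. The sentence opens with an exception for anything specified otherwise, the section closes by ruling out other imputation, and the primary analysis is specified separately as a logistic regression with the Week 16 response missing.

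**Conclusion.** The point holds as a fault of labelling and method in the primary analysis. The declared strategy is not the one applied, and the primary odds ratio is a complete-case estimate that leaves collected EASI unused. The consequence is conditional. Under the stated assumptions the odds ratio moves from 3.00 to about 2.7-2.8 or about 3.3, and it hardly moves (3.01) when the mechanism is the same in both arms.

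Three stronger readings go too far. Earlier EASI is not discarded throughout, because the GLMM uses it. Bias is not demonstrated: unequal drop-out alone does not shift the odds ratio if leavers would respond like completers. The 20% allowance is not the exposed fraction, because it covers all withdrawals and the non-related share is not given. The sample size is not in error. This should be corrected, but it does not by itself undermine the trial.

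**What to change.** - In Protocol 2.1 and SAP Table 1, rename the handling of non-related withdrawal as missing data under a stated missing-at-random assumption.
- For the primary analysis, impute Week 16 EASI within arm by multiple imputation from baseline EASI, vIGA and all off-rescue post-baseline EASI, then derive EASI-50. Keep the complete-case logistic regression as a sensitivity analysis.
- Bring in Early Termination EASI by actual study day, or through contiguous analysis windows mapped to the nearest scheduled visit. The ±3-day visit windows would miss most such visits.
- In SAP 9.4.2.2, remove the option to replace the EASI-50 GLMM with a Week 16-only logistic model where it serves as the sensitivity analysis for the primary endpoint.
- A tipping-point analysis, or one counting every withdrawal as non-response, would be a useful addition.

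The cost is SAP wording and standard programming, with no new data. The price is reliance on the missing-at-random assumption, which the sensitivity analyses would probe.

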7.1.2 Defined Data Point Sets

Efficacy data point sets 1-6 were designed to replicate the corresponding primary endpoint estimands intercurrent event strategies:

- EDPS1 corresponds to primary estimand 1.
- EDPS2 corresponds to supplementary estimand 1.
- EDPS3 corresponds to supplementary estimand 2.
- EDPS4 corresponds to supplementary estimand 3.
- EDPS5 corresponds to supplementary estimand 4.
- EDPS6 corresponds to supplementary estimand 5.

The following definitions and computational methods applied to the data point sets:

* TCS/TCI rescue therapy – is the rescue therapy when topical corticosteroid or calcineurin inhibitors medication was prescribed. Rescue therapy is reported in both the CRF and patient diary. For the analysis purposes rescue therapy recorded on CRF page will be used.

Multiple periods with rescue therapy are allowed during the study. All periods with rescue therapy are considered in EDPS definitions.

** Study withdrawal reasons related to study medication are lack of efficacy, treatment failure, adverse event (if related). Also, withdrawal of consent may be considered related to study medication based on the clarification text provided, that will be assessed by the Evelo team and provided in a separate spreadsheet. Type 2 prohibited medication will be considered as treatment withdrawal due to related reason at the date of medication start. Non-related reasons are all other reasons.

¹Last off-rescue observation is defined as the last off-rescue observation in the period before the corresponding intercurrent event plus early termination visit in case of early study discontinuation (off-rescue is defined as data collected at least 28 days after use of rescue medication or type 1 prohibited medication).

Categorization of all concomitant medications prescribed during the study will be done by Evelo clinician in order to identify TCS/TCI rescue therapy, antimicrobial rescue therapy and prohibited medications of type 1 and 2.

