7.1.2.1 Efficacy Data Point Set 1 (EDPS1)

EDPS1 consists of all data collected at a scheduled timepoint that is at least 28 days after use of TCS/TCI rescue therapy* or type 1 prohibited medication and before use of type 2 prohibited medication. Data collected less than 28 days after such use or data missing due to withdrawal from the study for reasons considered related to study medication** or data collected after use of type 2 prohibited medications will be replaced as follows:

- Continuous endpoints: value will be imputed with the last off-rescue¹ observation in the period before the event plus early termination visit in case of early study discontinuation (off-rescue is defined as data collected at least 28 days after use of rescue medication or type 1 prohibited medication)
- Responder endpoints: value will be imputed as non-response.
- Count endpoints: N/A (no count endpoint will use this DPS).

Data missing for other reasons, including early withdrawal from the study due to reasons not considered related to study medication will not be replaced and will be considered as missing.

Example 1: if patient completed 16 weeks of study with rescue therapy during week 3 and then during week 10 then responder endpoints will be analysed as shown in table:

Week 0	Week 2	Week 4	Week 8	Week 12	Week 16
As collected	As collected	Imputed as non-responder because there was a rescue therapy within 28 days before Week 4 visit	As collected	Imputed as non-responder because there was a rescue therapy within 28 days before Week 12 visit	As collected

Example 2: if patient completed 16 weeks of study with rescue therapy from Day 25 to Day 31 then responder endpoints will be analysed as shown in table:

Week 0	Week 2	Week 4	Week 8	Week 12	Week 16
As collected	As collected	Imputed as non-responder because there was a rescue therapy within 28 days before Week 4 visit	Imputed as non-responder because there was a rescue therapy within 28 days before Week 4 visit	As collected	As collected

Example 3: if patient withdrew study early due to the lack of efficacy after 12 weeks of treatment with rescue therapy during week 3 (unscheduled rescue therapy visit was not done) and then during week 10 (unscheduled rescue therapy visit was done at Week 9 prior to the rescue therapy start) then continuous endpoints will be analysed as shown in table:

Week 0	Week 2	Week 4	Week 8	Week 12	Week 16

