7.1.2.4 Efficacy Data Point Set 4 (EDPS4)

EDPS4 consists of EASI-50 responses collected at Week 16 that were evaluated at least 28 days after use of TCS/TCI rescue therapy* or type 1 prohibited medication and before use of type 2 prohibited medication. Data collected less than 28 days after such use will be replaced as per EDPS1. Data missing due to other reasons including early withdrawal from the study for any reason will not be replaced and be considered as missing. Data after use of type 2 prohibited medication will be considered missing.

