7.1.2.6 Efficacy Data Point Set 6 (EDPS6)

EDPS6 consists of data collected in the absence of TCS/TCI rescue therapy* and type 1 prohibited medication at any time since Day 1 for the responder endpoints relating to EASI, vIGA and PP-NRS. Data collected after such use will be imputed as non-response. Data missing due to withdrawal from the study for reasons considered related to study medication** and data after use of type 2 prohibited medication will be imputed as per EDPS1.

Responses missing for other reasons, including early withdrawal from the study due to reasons not considered related to study medication will not be replaced and will be considered as missing.

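### On the SAP's literal list, a withdrawal for worsening atopic dermatitis recorded as an unrelated adverse event leaves the primary model, and no planned analysis is specified to count it as non-response

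*SAP*

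**What the plan says.** SAP Section 9.3.1 (Table 1) splits discontinuation before Week 16 by reason. A related reason makes the participant a non-responder where data are missing; for a non-related reason the missing value is not replaced. The footnote says "Treatment discontinuation reasons will be checked" and then "Reasons related to study medication are lack of efficacy, treatment failure, adverse event (if related"). It allows one reclassification from free text: "withdrawal of consent may be considered related to study medication based on the clarification text provided", as assessed by the sponsor. SAP Section 7.1.2 repeats the list and closes it: "Non-related reasons are all other reasons". Under EDPS1 (SAP 7.1.2.1), data missing through "early withdrawal from the study due to reasons not considered related to study medication will not be replaced and will be considered as missing". On the primary logistic model, SAP 9.3.3 says "Only Week 16 data will be included in the model". Section 4.3 of the SAP Addendum carries the same intercurrent-event rules into Cohort 4.

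Protocol Section 2.1 makes non-responders of those who withdraw for reasons relating to study medication. Its examples are a related adverse event, lack of efficacy and the need for another therapy. Protocol Section 11.1.2 requires the reason for every premature withdrawal to be judged related or non-related before lock and unblinding. Protocol Sections 9.1 and 9.4.1 allow worsening of atopic dermatitis to be an adverse event when the change is considerable or clinically significant, and Section 9.4.3 has its causality judged against the IMP.

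**The concern.** The same clinical event can reach the analysis by two routes. Recorded as lack of efficacy, it is a non-response. Recorded as an adverse event that the investigator does not attribute to the IMP, it is a missing value. Worsening of the underlying disease can naturally be rated unrelated to the capsule, yet it bears directly on the endpoint. The primary model adjusts only for baseline factors and uses no earlier visits, so it cannot recover what is lost when the outcome itself causes the missingness.

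The SAP already accepts that a recorded reason can hide a treatment-related one, because it provides for this with consent withdrawal. It has no counterpart for adverse-event withdrawals. It also drops the protocol's third example, need for another therapy, from its list, and Section 13 does not log that change; the type 2 medication rule covers only part of it. At stake is whether membership of the primary analysis depends on a causality rating made for safety purposes.

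**Working it through.** **1. How narrow the case is.** It does not arise if any of these holds:
- the reason is coded lack of efficacy;
- the participant meets the treatment-failure definition (Protocol 5.4 and 6.9.1.2), which covers starting phototherapy, an oral agent, a biologic, or an intermediate or high-potency topical other than permitted rescue;
- a type 2 prohibited medication was used (SAP 7.1.2);
- a Week 16 assessment was obtained.

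The Early Termination visit cannot stand in for Week 16: SAP 7.7 keeps it out of analysis tables, with exceptions that do not supply a Week 16 response.

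**2. Whether another planned analysis catches it.**
- EDPS2, EDPS3 and EDPS5 reuse the related/non-related split.
- EDPS4: "Data missing due to other reasons including early withdrawal from the study for any reason will not be replaced and be considered as missing".
- EDPS6: "Responses missing for other reasons, including early withdrawal from the study due to reasons not considered related to study medication will not be replaced". The Table 2 wording for Supplementary Estimand 5 might reach participants with earlier TCS/TCI or type 1 use, but no others.
- The all-visit GLMM (SAP 9.3.4) uses earlier visits but does not set Week 16 to non-response.

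**3. The plan's own figure.** Inputs from SAP Section 6: 25% against 50%, two-sided 5%, 80% power. The uncorrected formula is n = [1.960 × √(2 × 0.375 × 0.625) + 0.842 × √(0.25 × 0.75 + 0.50 × 0.50)]² / 0.25² = 57.7, so 58 per group (power 80.2%). Then 58/0.80 = 72.5, so 73. Both stated figures reproduce. The classification gap does not touch this arithmetic; it changes who is analysed.

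**4. Size, as an illustration.** Take 75 per arm with 20% missing, which is 15 missing and 60 observed. Observed responders are 30/60 on active and 15/60 on placebo, so the reported odds ratio is (30/30)/(15/45) = 3.00. Let a (active) and b (placebo) of the missing be such withdrawals, and count them as non-responders:

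OR counted = 3.00 × (1 + b/45)/(1 + a/30)

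Reported relative to counted = (1 + a/30)/(1 + b/45)

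| a | b | Active | Placebo | OR counted | Reported 3.00 is off by |
|---|---|---|---|---|---|
| 1 | 0 | 30/61 = 49.2% | 25.0% | 2.90 | +3.3% |
| 0 | 1 | 50.0% | 15/61 = 24.6% | 3.07 | -2.2% |
| 3 | 0 | 30/63 = 47.6% | 25.0% | 2.73 | +10.0% |
| 0 | 5 | 50.0% | 15/65 = 23.1% | 3.33 | -10.0% |
| 5 | 0 | 30/65 = 46.2% | 25.0% | 2.57 | +16.7% |
| 5 | 5 | 46.2% | 23.1% | 2.86 | +5.0% |

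A 10% shift therefore needs 3 of the 15 missing on active (20%) or 5 of 15 on placebo (33%), with none on the other arm.

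With no true effect (15/60 in both arms, 45 non-responders each), five on active gives 45/50 = 0.90, five on placebo gives 50/45 = 1.11, and equal counts give 1.00.

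**5. Cohort 4 on the same basis.** With 20% missing, 56 of 70 active leaves 28 non-responders, 56 of 70 matched placebo leaves 42, and 28 of 35 concurrent placebo leaves 21. One case on active makes the reported ratio 1/28 = 3.6% too high. One on placebo gives 1/(1 + 1/42) = 0.977 against matched placebo, or 1/(1 + 1/21) = 0.955 against concurrent placebo only.

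**The case against.** The recorded reason is an input to a decision, not the decision. Every premature withdrawal is reviewed before unblinding (Protocol 11.1.2) and reasons are checked (SAP 9.3.1). The primary reason for withdrawal on the CRF (Protocol 5.4) is a separate item from the causality rating on the adverse event (Protocol 9.4.1), so an unrelated rating does not by itself fix the withdrawal reason. Treatment failure is broadly defined, topical rescue can be repeated without limit, and coding instructions may sit in CRF guidelines that are not part of these documents. Protocol 2.1 itself names only a related adverse event, so the SAP's qualifier follows its wording.

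Most of this stands, and it rules out two stronger readings. A reader might infer that such withdrawals are certain to be classed non-related; the documents do not support that, because the review can assign lack of efficacy. A reader might also infer a bias in favour of EDP1815; the documents give no frequency and no split by arm, and the table shows that either sign is possible.

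What does not fall away is that the review has no criterion for this case. A reviewer who applies the SAP list literally leaves the participant out; one who follows the aim of Protocol 2.1 may count a non-response. No planned output would show how much that choice matters.

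**Conclusion.** The point holds in this limited form. The SAP's closed list can remove outcome-driven withdrawals from the primary model, its one text-based correction does not cover adverse-event withdrawals, and no planned analysis is specified to count them as non-response. It should be settled before lock; it does not threaten the design. One case moves the Cohorts 1-3 odds ratio by about 2% to 3%, and a 10% shift needs three on active alone or five on placebo alone.

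These sizes assume the planning rates, exactly 20% missing per arm, an unadjusted odds ratio, and counts chosen for illustration. Cases spread across arms largely offset one another. It would go too far to say that the SAP contradicts the protocol: the protocol's list is given as examples and includes the relatedness qualifier.

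**What to change.** 1. Keep the primary model and add one sensitivity analysis of the primary endpoint that counts every missing Week 16 EASI-50 as non-response. The cost is one output for Cohorts 1-3 and one for Cohort 4. Its downside is that it also counts values missing for other causes. If all of the planned 20% drop-out were missing, rates would go from 25% and 50% to 15/75 = 20% and 30/75 = 40%, and the odds ratio from 3.00 to 0.667/0.25 = 2.67. It should therefore stay a sensitivity analysis.
2. In SAP Section 7.1.2 and the footnotes to Tables 1 and 2, extend the text-based review from consent withdrawal to adverse-event withdrawals. Where the recorded text shows worsening of atopic dermatitis, assign the withdrawal to lack of efficacy (related, non-responder) whatever its IMP causality rating, decided blinded before database lock. Cohorts 1-3 may be locked and unblinded before Cohort 4 (SAP 5.2), so the rule has to be in place before the first lock. The cost is one sentence in three places and an entry in Section 13. The downside is that this is partly an estimand choice: Protocol 1.1 notes that flares often have external triggers, and some of those would count as non-response.
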